14.3.9 Analysis of secondary endpoints

Analysis of secondary endpoints

- Number of AEs from baseline to Week 16+3 days per subject.

is described in detail in Section [14.3.14.1](#).

14.3.10 Analysis of exploratory endpoints

Continuous endpoints

- EASI at each visit from Week 1 to Week 16.
- SCORAD at each visit from Week 1 to Week 16.
- Change in ADSD score (weekly average) from baseline to Week 16.
- Change in each ADSD individual symptom score (weekly average) from baseline to Week 16.

will be summarized descriptively at each visit by treatment group and will be analyzed using an MMRM. The model will include treatment, visit, visit by treatment interaction terms, region (Japan, non-Japanese countries), and baseline disease severity (EASI score at baseline ≤ 16 and ≥ 16.1) as factors and adjust for the baseline value of the endpoint of interest as a covariate. For the analysis of the EASI score at each visit, the baseline disease severity factor will be excluded from the MMRM in order to avoid introducing a discontinuity in the relationship between the post-baseline EASI scores and the baseline EASI score. The model

will use an unstructured covariance matrix, and the Kenward-Roger approximation to estimate the denominator degrees of freedom. The SAP will specify alternative structures for the covariance matrix, to be used in case of non-convergence. For these endpoints, data collected after permanent discontinuation of IMP or after initiation of rescue medication will be excluded from the analysis and 'treated as missing'. Missing data will be assumed to be MAR. The estimates will be presented with 95% CIs and nominal p-values at each visit.

Binary endpoints

- Having a decrease in EASI of at least 50% (EASI 50) from baseline to Week 16.
- Having a decrease in EASI of at least 75% (EASI 75) from baseline to Week 16.
- Having a decrease in EASI of at least 90% (EASI 90) from baseline to Week 16.
- Having vIGA-AD of 0 (clear) or 1 (almost clear) at Week 16.
- Having a decrease in vIGA-AD of at least 2 points from baseline to Week 16.
- Having a decrease in ADSD **CCI** score (weekly average) of at least 4 points from baseline to Week 16 in subjects with ADSD **CCI** score ≥ 4 at baseline.

will be summarized descriptively at each visit by treatment group and will be analyzed based on a logistic regression model, including region (Japan, non-Japanese countries) and baseline disease severity (EASI score at baseline ≤ 16 and ≥ 16.1) as factors and adjusting for the baseline value of the endpoint as a covariate. The logistic regression model will be used to estimate the risk difference and associated 95% confidence interval based on the standardized estimator presented in Ge et al. (68). For the analysis of the EASI responder endpoints, baseline disease severity will not be included as a factor in the logistic regression model. Subjects who prior to the Week 16 visit received rescue treatment or permanently discontinued IMP or have missing data will be considered as non-responders.

Time-to-event endpoint

- Time from randomization to having an observed decrease in EASI of at least 50% (EASI 50) from baseline.
- Time from randomization to having a decrease in ADSD **CCI** score (weekly average) of at least 4 points from baseline in subjects with ADSD **CCI** score ≥ 4 at baseline.

will be analyzed according to Gray's test, stratified by region (Japan, non-Japanese countries) and baseline disease severity (EASI score at baseline ≤ 16 and ≥ 16.1). Gray's test accounts for the occurrence of the competing risks, permanent discontinuation of IMP and initiation of

rescue medication. Inference will be based on the estimated cumulative incidence functions derived from the Aalen-Johansen estimator. The estimated cumulative incidence functions will be presented by treatment group along with pointwise 95% confidence intervals. In addition, the estimated sub-distributional hazard ratio from a Fine and Gray model, stratified by region (Japan, non-Japanese countries) and baseline disease severity (EASI score at baseline ≤ 16 and ≥ 16.1) and adjusted for the baseline value of the endpoint of interest, will be presented along with the corresponding 95% CI.

The following sleep **CCI** and nocturnal **CCI** endpoints will be collected using actigraphy:

- Change in **CCI** from baseline to Week 16. The endpoint is measured in minutes and weekly averages will be reported.
- Change in number of nocturnal **CCI** events per hour from baseline to Week 16. The endpoint will be assessed daily and the weekly averages will be reported.
- Change in duration of nocturnal **CCI** events per hour from baseline to Week 16. The endpoint will be assessed daily and the weekly averages will be reported.
- Change in **CCI** from baseline to Week **CCI CCI** is calculated as the proportion of time spent **CCI** versus total time **CCI**, expressed as a percentage. This will be assessed daily and weekly averages will be reported.

These endpoints will be summarized descriptively by week and treatment group. The weekly average of data collected using actigraphy will be based on data collected over 7 days. Data collected after the initiation of rescue medication or permanent discontinuation of IMP will be excluded from the calculation of the weekly averages. In order to calculate the weekly average, a minimum of 4 out of the 7 planned measurements will be required.

The following sleep disturbance endpoints will be collected using the eDiary and summarized descriptively by week and treatment group:

- Difficulty **CCI** at Week **CCI**
- Frequency of **CCI** During the Night at Week **CCI**
- **CCI** at Week **CCI**
- **CCI** at Week **CCI**

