To evaluate effect of treatment with LEO 152020 compared with placebo for up to 16 weeks of treatment on PROs in subjects with moderate to severe AD	Exploratory endpoints 
 Change in POEM from baseline to Week 16. Change in DLQI from baseline to Week 16. Having a decrease in DLQI of at least 4 points from baseline to Week 16 in subjects with DLQI ≥ 4 at baseline. Change in EQ-5D-5L from baseline to Week 16. Change in HADS from baseline to Week 16. Change in WPAI:AD (for each individual domain) from baseline to Week 16. Having a decrease in POEM of at least 4 points from baseline to Week 16 in subjects with POEM ≥ 4 at baseline.
Exploratory objectives (continued)	
To evaluate pharmacokinetic parameters of LEO 152020 for up to 16 weeks of treatment in subjects with moderate to severe AD	Exploratory endpoint 
 C_{trough} of LEO 152020 at Weeks CCI . C_{max} of LEO 152020 at Weeks CCI .

Objectives	Endpoints

To evaluate effect of treatment with LEO 152020 compared with placebo for [CCI] of treatment on disease biomarkers and biomarkers related to the mechanism of action of LEO 152020 in subjects with moderate to severe AD
	
Exploratory endpoints
 
 • Change in expression levels of blood biomarkers from baseline to [CCI] • Change in expression levels of AD disease biomarkers in skin from baseline to [CCI]

To explore the effect of treatment with LEO 152020 compared with placebo for [CCI] of treatment on sleep disturbance and nocturnal [CCI] in subjects with moderate to severe AD
	
Exploratory endpoints
 
Based on eDiary data
 
 • Difficulty [CCI] at Week [CCI] • Frequency of [CCI] During the Night at Week [CCI] • [CCI] at Week [CCI] • [CCI] at Week [CCI] 
Based on actigraphy data
 
 • Change in [CCI] from baseline to Week [CCI] • Change in [CCI] from baseline to Week [CCI] • Change in number of nocturnal [CCI] events per hour from baseline to Week [CCI] • Change in duration of nocturnal [CCI] per hour from baseline to Week [CCI]

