7.1 Overall trial design

Overview

This is a phase 2 randomized, triple-blind, placebo-controlled, parallel-group, international trial to evaluate the efficacy and safety of orally-administered LEO 152020 tablets

(**CCI** **CCI** and **CCI** compared with placebo tablets for up to 16 weeks of treatment in adults with moderate to severe AD.

The trial will consist of:

- A screening period of maximum 5 weeks (at the earliest Week -5 to baseline) including a run-in period of 1 week (Week -1 to baseline).
- A treatment period of 16 weeks (baseline to Week 16).
- A safety follow-up period of 7 days (Week 16 to Week 17).

Randomization will take place at baseline. The primary endpoint will be assessed at Week 16. The final safety assessments will be conducted at Week 17.

The subject's visit schedule and the assessments/procedures to be conducted at each visit are presented in Section 4. The trial rationale is presented in Section 5.3 and the scientific rationales for trial design are presented in Section 12.1.

Screening period

In the screening period, eligibility of the subject to participate in the trial will be evaluated. From the screening visit, the subject will be asked to stop any systemic AD treatment (Section 8.3 and Section 9.7).

The screening period will include a run-in period (Week -1 to baseline). From the run-in visit (Week -1), the subject will be asked to stop any topical AD treatment with TCS, TCI, PDE4i, and/or topical JAK inhibitors and to apply an emollient (background treatment, Section 9.4). The subject will be asked to apply the emollient at least twice daily and for at least 7 days prior to the planned randomization (baseline).

At the run-in visit, the subject will receive an eDiary and training in using the device. From Week -1, the subject will be asked to complete the eDiary for 7 days prior to randomization (Section 11.5.1).

At the run-in visit, subjects who consented to participate in wristband actigraphy will receive 2 actigraphy devices. From Week -1, the subjects will be asked record scratch and sleep data with the devices daily (Section 11.7).

The total duration of the screening period including the run-in period will depend on the time needed for washout of the systemic AD treatment(s) by baseline and may last for a maximum of 5 weeks, as applicable. It will be recorded in the eCRF if washout was required and which treatment(s) were stopped.

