11.7.2 Wristband scratch and sleep monitoring

Subjects participating in this optional component of the trial will be the first approximately 100 subjects who provide additional consent for this assessment.

At Week -1, the subject will receive 2 wristband actigraphy devices (CCI [REDACTED], CCI [REDACTED]) together with instructions for use. From Week -1 to Week 16, the subject will be asked to wear 1 device on each wrist daily and without interruption. If this is too inconvenient, the device worn on the subject's dominant wrist should at least be worn at nighttime during the subject's standard sleep period. If necessary, a hypoallergenic bandage can be placed under each device to prevent skin irritation. The devices are water resistant and do not need to be removed for showering or bathing but should be removed when spending an extended time in the water (e.g. when swimming).

At each visit between Week -1 and Week 16, the subject will be asked to bring the devices back to the site for data transfer using the CCI [REDACTED] software. The devices can record 30 days of data at a time. Therefore, the time between consecutive visits should not exceed 30 days and special attention should be paid in case of missed visits.

The wristband actigraphy devices contain a tri-axial accelerometer sampling motion (in units of acceleration, g) at a rate of 20 Hz. Actigraphy data will be processed in Rapid Actigraphy Data Analyzer software (CCI [REDACTED]). First, the segmentation algorithm (51) will be applied which objectively differentiates active, major rest, minor rest, and missing data periods (during which the device was not worn). Within the major rest periods, which represent time for the main sleep period, the CCI [REDACTED] algorithm (52) and sleep/wake algorithm (53) will be applied. The CCI [REDACTED] algorithm will quantify individual CCI [REDACTED] events used to generate CCI [REDACTED] endpoints including the number of events per hour and the duration (in seconds) of events per hour. The CCI [REDACTED] algorithm uses movement to estimate CCI [REDACTED] versus CCI [REDACTED] and will be used to generate CCI [REDACTED] endpoints including CCI [REDACTED] (percentage of the major rest period spent CCI [REDACTED] CCI [REDACTED] (in minutes), and nocturnal CCI [REDACTED]).

Reporting in eCRF

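### The four actigraphy change endpoints have no pre-specified, baseline-adjusted difference from placebo, although their exploratory objective is a comparison with placebo

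*Combined protocol and SAP*

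**What the plan says.** Section 14.3.10 lists four continuous actigraphy endpoints, each a change from baseline built on weekly averages, and gives one analysis: "These endpoints will be summarized descriptively by week and treatment group". Under Section 14.3.1 that means mean, median, SD, quartiles and range by arm, on observed cases. Two data rules follow: "In order to calculate the weekly average, a minimum of 4 out of the 7 planned measurements will be required", and "Data collected after the initiation of rescue medication or permanent discontinuation of IMP will be excluded from the calculation of the weekly averages".

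The objective in Section 6, Panel 4 is comparative: "To explore the effect of treatment with LEO 152020 compared with placebo for" a stated period, on sleep disturbance and nocturnal events.

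A baseline is collected. Section 7.1 says of consenting subjects: "From Week -1, the subjects will be asked record scratch and sleep data with the devices daily". Section 12.1 gives establishing a baseline for these data as one purpose of the run-in week. Section 14.2 defines an analysis set, FAS_actigraphy. Participants, per Section 11.7.2, "will be the first approximately 100 subjects who provide additional consent for this assessment". Appendix 4 states that the component is not available in Japan.

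Elsewhere the plan models its continuous change endpoints. In 14.3.10 the ADSD changes get an MMRM with treatment, visit, their interaction, region and severity "as factors and adjust for the baseline value of the endpoint of interest as a covariate". Section 14.3.11 uses the same MMRM for POEM, DLQI and EQ-5D-5L, and an ANCOVA with treatment, region, severity and baseline score for HADS and WPAI:AD.

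**The concern.** The objective asks how LEO 152020 compares with placebo, but the stated output is four columns of raw change. Anyone wanting the comparison must subtract arm means. That estimator is less precise than a baseline-adjusted one, and it carries any chance baseline difference into the result through regression to the mean. Both effects matter more here than in the full trial because the arms are small.

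The plan already has the pieces of a better analysis: a recorded baseline week, a defined analysis set and a model used for comparable endpoints. It gives no reason for treating actigraphy differently. What is at stake is precision and a comparison fixed before unblinding, in a component that asks about 100 subjects to wear two devices from Week -1 to Week 16.

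**Working it through.** **No stated figure to reproduce.** The plan gives no sample size derivation, SD, effect or power for actigraphy. The size of the point therefore depends on an assumed correlation, shown as a range.

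**Inputs**
- About 100 participants (Section 11.7.2).
- Allocation 4:3:3:4 (Section 9.3.1). Expected arms: 100 × 4/14 = 28.6 and 100 × 3/14 = 21.4, that is about 29/21/21/29.
- Correlation ρ between the baseline and endpoint-week averages: **assumed**, 0.3 to 0.8. The value 0.65 appears in Section 14.1, but for EASI in the lower-severity stratum, so it is only a reference point.
- Equal SDs at both times (assumed). Results are in units of that SD.

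**Formulas**
- Per-subject variance, raw change: 2(1 − ρ).
- Per-subject variance, baseline-adjusted: 1 − ρ².
- Ratio: (1 − ρ²) / [2(1 − ρ)] = (1 + ρ)/2.
- 95% CI half-width: 1.96 × √[V × (1/n₁ + 1/n₂)].

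Example at ρ = 0.5, larger active arm against placebo: 1/28.57 + 1/28.57 = 0.070. Raw change: 1.96 × √(1.00 × 0.070) = 0.52. Adjusted: 1.96 × √(0.75 × 0.070) = 0.45.

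| Assumed ρ | Variance ratio | Half-width, 28.6 v 28.6: raw → adjusted | Half-width, 21.4 v 28.6: raw → adjusted | Participants needed on raw change to match 100 adjusted |
|---|---|---|---|---|
| 0.3 | 0.65 | 0.61 → 0.49 | 0.66 → 0.53 | 100/0.65 = 154 |
| 0.5 | 0.75 | 0.52 → 0.45 | 0.56 → 0.49 | 100/0.75 = 133 |
| 0.65 | 0.825 | 0.43 → 0.39 | 0.47 → 0.43 | 100/0.825 = 121 |
| 0.8 | 0.90 | 0.33 → 0.31 | 0.35 → 0.34 | 100/0.90 = 111 |

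**Fewer evaluable subjects.** The 4-of-7 rule and the exclusion after rescue or discontinuation will reduce n. At ρ = 0.5 in the larger active arm, half-widths are 0.58 → 0.50 with 80 evaluable and 0.67 → 0.58 with 60. The ratio does not change.

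**Chance baseline differences.** The SD of a difference in baseline means is √(1/29 + 1/29) = 0.263 for 29 v 29 and √(1/21 + 1/29) = 0.287 for 21 v 29. The probability of a gap above 0.3 SD in either direction is about 25% and 30% respectively. A 0.3 SD gap moves the raw-change difference away from the adjusted one by (1 − ρ) × 0.3, which is 0.15 SD at ρ = 0.5.

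**Missing data.** Section 14.3.2 states a missing-at-random assumption for endpoints analysed by MMRM, and no missing-data approach is given for actigraphy. The raw means at the endpoint week describe only subjects still on IMP without rescue who have a valid weekly average, a group that may differ by arm. A repeated-measures model would also use those subjects' earlier weeks.

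**The case against.** The strongest reply is that descriptive reporting is a legitimate choice for an optional, unpowered component. Section 11.7.1 calls the optional assessments exploratory and sends them to an addendum to the trial report. The eDiary sleep endpoints under the same objective are also only summarized, and actigraphy lies outside the testing strategy. All of this stands and keeps the point minor. It does not explain why these continuous changes are handled differently from HADS or WPAI:AD, which are exploratory too.

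Four stronger readings are tempting, and the documents do not support them.

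- **That the objective goes unanswered.** The objective is to explore. Arm means, SDs and numbers allow an unadjusted difference and CI. The loss is precision and a pre-specified contrast.
- **That self-selection unbalances the arms.** Devices are issued at the run-in visit to subjects who have already consented, before randomization, so arms within the subset remain randomized. Self-selection limits generalisability. The greater exposure to chance imbalance comes from small arms alone.
- **That baseline is ignored.** It enters through the change score, but not as a covariate.
- **That no comparison will ever be made.** Section 14.3.13 leaves further exploratory analyses to the SAP, and no separate SAP text is in the combined document. The point can be made about the protocol text only.

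A claim about power would need an assumed effect as well as a correlation, so none is made here.

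**Conclusion.** The point holds as a minor one. The protocol text pre-specifies no active-minus-placebo estimate for the four actigraphy endpoints and uses neither the Week -1 weekly average nor the severity stratum as a covariate, against a comparative objective and its own practice for similar endpoints.

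Baseline adjustment would cut the variance of each difference by 35% at an assumed ρ of 0.3, falling to 10% at 0.8 (25% at 0.5). These figures assume equal SDs at both times and a linear relation to baseline. They exclude any further gain from the severity stratum or from intermediate weeks. The benefit is modest if the measures are highly correlated over time. No primary or secondary conclusion depends on it.

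**What to change.** In Section 14.3.10, or in the SAP before the randomization code is broken, keep the descriptive summaries and add for each actigraphy endpoint, in FAS_actigraphy:

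- the section's existing MMRM applied to the weekly averages, with treatment, week, treatment by week and baseline EASI severity (≤16, ≥16.1) as factors and the Week -1 weekly average as covariate; or, for the endpoint week only, the 14.3.11 ANCOVA with treatment, severity and that covariate;
- no region term, since actigraphy is not available in Japan;
- each active-minus-placebo difference with its 95% CI, labelled exploratory and outside the gatekeeping procedure.

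The MMRM suits the data better, because HADS and WPAI:AD are scheduled only at baseline and Week 16 (apart from early termination and unscheduled visits), whereas actigraphy runs throughout. One practical caution: an unstructured covariance over 16 weekly averages has 16 × 17/2 = 136 parameters for about 100 subjects. The set of weeks modelled, or the fallback structure that 14.3.10 already leaves to the SAP, should be named in advance.

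The cost is a short paragraph and four tables, with no new data. It adds 4 endpoints × 3 contrasts = 12 comparisons without multiplicity control. If they were independent, the chance of at least one nominal false positive would be 1 − 0.95¹² = 46%. They are correlated, which lowers this, but it is a reason to lead with estimates and intervals.

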14.3.11 Analysis of patient-reported outcomes

Continuous endpoints

- Change in POEM from baseline to Week 16.
- Change in DLQI from baseline to Week 16.
- Change in EQ-5D-5L from baseline to Week 16.

will be summarized descriptively by week and treatment group and will be analyzed using the same MMRM model described in Section 14.3.10 for continuous endpoints.

The following endpoints

- Change in HADS from baseline to Week 16.
- Change in WPAI:AD (for each individual domain) from baseline to Week 16.

will be analyzed using an ANCOVA model including treatment, region (Japan, non-Japanese countries), and baseline disease severity (EASI score at baseline ≤ 16 and ≥ 16.1) as factors and adjusted for the baseline score as covariate. Data collected after the occurrence of an intercurrent event will be excluded from the analysis and "treated as missing". Missing data will be assumed to be MAR.

Binary endpoints

- Having a decrease in DLQI of at least 4 points from baseline to Week 16 in subjects with $DLQI \geq 4$ at baseline.
- Having a decrease in POEM of at least 4 points from baseline at Week 16 in subjects with $POEM \geq 4$ at baseline.

will be summarized descriptively at each visit by treatment group and will be analyzed using the same logistic regression model described in Section 14.3.10 for binary endpoints.

14.3.12 Analysis of pharmacodynamics

Exploratory analyses for the following endpoints will be conducted for the total population as well as by baseline disease severity (EASI score at baseline ≤ 16 and ≥ 16.1)

- Change in expression levels of blood biomarkers from baseline to Week **CC**
- Change in expression levels of AD disease biomarkers in skin from baseline to Week **CC**

The biomarker results will be reported in an addendum to the CTR. If biopsies are collected from less than 10% of the randomized subjects in a specific treatment group, analysis may not be carried out for that treatment group as the number of biopsies may be too low to allow for a meaningful analysis.

14.3.13 Exploratory analyses

Additional exploratory analyses will be described in the SAP and will be conducted if deemed necessary.

14.3.14 Analysis of safety

The analysis of safety will be based on the safety analysis set.

14.3.14.1 Adverse events

AEs will be coded during the trial according to MedDRA. AEs will be presented by preferred term and primary SOC.

Treatment-emergent AEs will be summarized; however, all AEs recorded during the trial will be included in subject data listings. Treatment-emergent and non-treatment-emergent AEs will be listed separately. An event will be considered treatment-emergent if started after the first dose of IMP or if started before the first dose of IMP and worsened in severity after first dose of IMP. An event will not be considered treatment-emergent if started 3 days after the last dose of IMP. The tabulations described below will only include the treatment-emergent AEs. In each of the tabulations, AEs are defined by MedDRA preferred terms within primary SOC.

AEs will be summarized in terms of the number of subjects with at least 1 event, the percentage of subjects with at least 1 event, the number of events, and the event rate per 100 patient years of observation time.

Related AEs are defined as AEs for which the investigator has not described the causal relationship to IMP as ‘not related’.

An overall summary of the number of events and the number (percentage) of subjects with any treatment-emergent AEs, deaths, SAEs, AESIs, permanent discontinuations from IMP and/or withdrawals from the trial due to AEs, treatment-related AEs, mild and moderate AEs and severe AEs will be presented.

Tabulations by SOC and preferred term will be presented by treatment group for all AEs, SAEs, related AEs, AESIs, and AEs leading to permanent discontinuation of IMP and/or withdrawal from trial. In addition, all AEs will be presented by severity and causal relationship to IMP, respectively.

The number of AEs and number of subjects with each type of AE (as described in the paragraph above) will be tabulated by treatment group from baseline to Week 16+3 days.

SAEs will be evaluated separately and a narrative will be given.

AESIs will be tabulated and listed by treatment group, no narratives will be given except if these are serious.

AEs leading to withdrawal from trial and/or permanent discontinuation of IMP will be tabulated and listed. The detailed listing will provide an overview of the individual cases and include the age and sex of the subject, treatment received at the time of AE onset, the AE preferred and reported terms, causality and severity of the AE, the action taken with the IMP, AE outcome, start and stop date of AE, duration of AE, and number of days since first and last administration of IMP. No narratives will be given.

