
To explore the exposure-response relationship of LEO 152020 and evaluate efficacy of LEO 152020 compared with placebo for up to 16 weeks of treatment in subjects with moderate to severe AD (continues)
	
Primary endpoint
 
 • Change in EASI from baseline to Week 16. 
Exploratory endpoints
 
 • EASI at each visit from Week 1 to Week 16. • Having a decrease in EASI of at least 50% (EASI 50) from baseline to Week 16. • Time from randomization to having an observed decrease in EASI of at least 50% (EASI 50) from baseline. • Having a decrease in EASI of at least 75% (EASI 75) from baseline to Week 16. • Having a decrease in EASI of at least 90% (EASI 90) from baseline to Week 16. • Having vIGA-AD of 0 (clear) or 1 (almost clear) at Week 16. • Having a decrease in vIGA-AD of at least 2 points from baseline to Week 16. • SCORAD at each visit from Week 1 to Week 16. • Change in ADSD score (weekly average) from baseline to Week 16. • Change in each ADSD individual symptom score ^a (weekly average) from baseline to Week 16. • Having a decrease in ADSD CCI score (weekly average) of at least 4 points from baseline to Week 16 in subjects with ADSD CCI score ≥ 4 at baseline.

Objectives	Endpoints
Primary objective (continued)	
To explore the exposure-response relationship of LEO 152020 and evaluate efficacy of LEO 152020 compared with placebo for up to 16 weeks of treatment in subjects with moderate to severe AD (continued)	
 Time from randomization to having a decrease in ADSD CCI score (weekly average) of at least 4 points from baseline in subjects with ADSD CCI score ≥ 4 at baseline.
Secondary objectives	
To evaluate the safety of LEO 152020 compared with placebo in subjects with moderate to severe AD	Secondary endpoints 
 Number of AEs ^b from baseline to Week 16+3 days per subject.
Exploratory objectives (continues)	

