Abbreviations: AD = atopic dermatitis; ADSD = Atopic Dermatitis Symptom Diary; AE = adverse event; C_{max} = maximum serum concentration; C_{trough} = lowest IMP concentration before the next dose of IMP is administered; DLQI = Dermatology Life Quality Index; EASI = Eczema Area and Severity Index; EASI 50 = decrease in EASI of at least 50% from baseline; EASI 75 = decrease in EASI of at least 75% from baseline; EASI 90 = decrease in EASI of at least 90% from baseline; ECG = electrocardiogram; EQ-5D-5L = EuroQoL 5-Dimension Health Questionnaire 5 Level; HADS = Hospital Anxiety and Depression Scale; IMP = investigational medicinal product; POEM = Patient-oriented Eczema Measure; PRO = patient-reported outcome; [CCI]; [CCI]; [CCI]; SCORAD = Scoring Atopic Dermatitis; vIGA-AD = Validated Investigator Global Assessment Scale for Atopic Dermatitis; [CCI]; WPAI:AD = Work Productivity and Activity Impairment Questionnaire: Atopic Dermatitis.

^a Includes [CCI]

^b Treatment emergent AEs (Section 14.3.14.1).

7 Trial design

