10.1 General principles

If the subject, the investigator, or LEO Pharma considers that it is not in the subject's best interest to continue treatment with the IMP or participate in the trial altogether, a subject may at any time:

- Permanently discontinue IMP (but continue to participate in trial-related activities as described in Section 10.3).
- Or withdraw from the trial (and thereby stop participating in further trial-related activities. Subjects will be encouraged to attend safety assessments to the extent possible to leave the trial in all safety [Section 10.3]).

Subjects who permanently discontinue IMP or withdraw from the trial will not be replaced.

If a subject withdraws from the trial, they may request destruction of any samples taken and not tested. The investigator must document this in the subject's medical record and inform LEO Pharma.

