14.3.6 Exposure and treatment compliance

The duration of exposure to treatment in a specific week interval will be calculated as the number of days from date of first dose of IMP in that period to the date of last dose of IMP in that period, both days included.

Exposure to treatment will be presented for the safety analysis set as days of exposure per treatment group.

The average number of weekly doses of IMP and the average total number of doses of IMP administered will be presented for the SAF by treatment group for week of treatment intervals and for the whole treatment period, respectively.

Treatment compliance will be presented for the SAF for each treatment group as the percentage of missed doses of IMP.

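### The AE endpoint names a fixed window to Week 16+3 days but counts only events up to 3 days after last dose, and the observation time used for AE rates is undefined

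*Combined protocol and SAP*

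**What the plan says.** Section 14.3.9 gives the secondary endpoint as "Number of AEs from baseline to Week 16+3 days per subject". Section 6, Panel 4 has the same endpoint, with a footnote restricting it to treatment-emergent AEs. Section 14.3.14.1 repeats the fixed window: numbers of AEs, and of subjects with AEs, "will be tabulated by treatment group from baseline to Week 16+3 days".

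The cut-off for counting an event is individual: "An event will not be considered treatment-emergent if started 3 days after the last dose of IMP". The tabulations contain treatment-emergent events only. Other AEs go into a separate listing.

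Section 14.3.14.1 also reports "the event rate per 100 patient years of observation time". The text we have does not say when observation time starts or ends, or how time after stopping IMP is treated. Section 14.3.6 deals with exposure as a different quantity ("Exposure to treatment will be presented for the safety analysis set as days of exposure per treatment group") and does not make it the denominator for AEs.

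Under Section 10.1 a subject may "Permanently discontinue IMP (but continue to participate in trial-related activities" or withdraw altogether. Section 10.3 asks those who only stop IMP to attend the nominal Week 16 visit, and Section 10.4 encourages them to keep their visit schedule. Section 13.2 has AEs collected until the subject completes the trial.

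**The concern.** For a subject who completes treatment the two limits agree to about a day, since the last dose is taken the evening before the Week 16 visit. For an early stopper who stays they separate. Someone stopping on Day 28 has a treatment-emergent cut-off at Day 31, while the named window runs to Day 115 (112 + 3). That leaves 84 days, or 12 weeks, in which AEs are collected and lie inside the endpoint's window but enter no table.

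The rate can suffer in the same way. If observation time means time in the trial, it includes weeks in which no event can enter the numerator.

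Comparing safety with placebo is the secondary objective, and stopping may well differ by arm. Section 10.2 lists AEs, systemic rescue and QTcF thresholds among the reasons for stopping, and these could act in either direction. Amendment 3 (Appendix 10) ended automatic withdrawal of subjects who stop IMP. It reworked the efficacy estimands to use the later data, but its log shows no matching change to the AE section.

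**Working it through.** The plan attaches no rate, power or margin to this endpoint, so there is no figure to reproduce. The check is a person-time calculation.

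**Inputs.** From the documents: the window is 16 + 3/7 = 16.43 weeks; the cut-off is last dose + 3 days; follow-up after withdrawal ends about 7 days after last dose (Section 10.3). Assumed: the same constant AE rate in every arm; a fraction d stops at Week 6; the rest complete. The intercurrent-event rates in Section 14.1 are redacted, so d is varied.

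**Time in which an AE can count**, per subject: (1 − d) × 16.43 + d × 6.43 weeks.

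- d = 5%: 15.93
- d = 15%: 14.93
- d = 25%: 13.93

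**Count per subject.** Under a constant rate the expected count is proportional to this time, so 25% versus 5% stopping gives 13.93 / 15.93 = 0.87. This does not depend on how observation time is defined.

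**Rate, one arm.** If observation time runs to Week 16+3 days and all stoppers stay, 15% stopping gives 14.93 / 16.43 = 0.909, about 9% too low.

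**Rate, 5% versus 25% stopping.** Each share is countable weeks divided by observed weeks.

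| Observation time | Weeks, 5% arm | Weeks, 25% arm | Share, 5% | Share, 25% | Ratio |
|---|---|---|---|---|---|
| To Week 16+3 days, all stoppers stay | 16.43 | 16.43 | 0.970 | 0.848 | 0.87 |
| Half stay, half leave 7 days after last dose | 16.19 | 15.25 | 0.984 | 0.913 | 0.93 |
| All stoppers withdraw | 15.96 | 14.07 | 0.998 | 0.990 | 0.99 |
| Ends at the treatment-emergent cut-off | 15.93 | 13.93 | 1 | 1 | 1.00 |

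Row 2 gives stoppers (16.43 + 7) / 2 = 11.71 weeks; row 3 gives them 7 weeks. If completers are observed to Week 17 instead, row 3 becomes 16.5 and 14.5 weeks and the ratio is 0.995.

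**Range.** For pairs 15% v 5%, 20% v 10%, 30% v 10% and 40% v 10%, stopping between Day 14 and Day 84, the count ratio runs from 0.72 (40% v 10%, Day 14) to 0.975 (Day 84 with a 10-point difference). Equal stopping gives 1.00.

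**Stops caused by AEs.** Take a background of 1.5 AEs per full window and add one treatment-emergent AE for each excess stop (0.25 − 0.05 = 0.20 per subject). The counts are 1.5 × 0.848 + 0.20 = 1.47 and 1.5 × 0.970 = 1.45, a ratio of 1.01. The arm with more stops no longer looks better. Dilution is still present: over matched time the ratio is (1.47 / 13.93) / (1.45 / 15.93) = 1.16, and 1.16 × 0.87 = 1.01.

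**The case against.** The strongest reply is that the denominator is undefined, not shown to be wrong. A reader might infer that numerator and denominator demonstrably mismatch; the documents do not support that. Section 14.3.1 leaves the SAP to be finalized before unblinding, and if observation time is set to end at the treatment-emergent cut-off the rate is unbiased. This stands, and the rate part of the point is therefore conditional.

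A reader might also infer that an arm with more discontinuations will look safer. That does not follow. It requires stoppers to stay in the trial for the rate effect, and stopping to be unrelated to AEs for the direction. Section 10.1 allows withdrawal, Section 10.4 only encourages continued visits, and AEs are a listed reason for stopping.

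Counting treatment-emergent events only is ordinary practice, and Week 16+3 days can be read as the outer bound of an on-treatment rule. That is a fair reading, but the endpoint's wording does not state it.

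There are safeguards. Later AEs are listed, SAEs receive narratives, AEs leading to discontinuation are tabulated, and disposition is shown by arm. The endpoint is descriptive, with no test attached. These limit the consequence. They do not define the denominator, and they do not put the later AEs of early stoppers in a table.

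**Conclusion.** The point holds in a limited form. Two things are on the page: the fixed endpoint window and the individual treatment-emergent cut-off differ for early stoppers who stay in the trial, and observation time has no definition. The per-subject count is lower in an arm with more early stopping whatever definition is later chosen. The rate is diluted only if observation time continues past the cut-off, as the words literally allow.

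Assuming equal true AE rates, Week 6 stops and all stoppers staying, the rate is understated by about 9% at 15% stopping, and the between-arm ratio is about 0.87 at 5% versus 25%. The rate effect is close to zero if stoppers withdraw, and the observed comparison can reverse if AEs cause the stops. None of the stopping rates comes from the plan.

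A reader dividing by 17 weeks would get 14.93 / 17 = 0.878, a 12% understatement. That is too large as a measure of early stopping: with no one stopping, 16.43 / 17 is already 0.966, so about 3 of the 12 points have another source.

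This is worth correcting before unblinding, but it does not threaten a formal conclusion of the trial.

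**What to change.** In Section 14.3.14.1 and the SAP:

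1. Define patient-years as first dose to the earlier of last dose + 3 days and last contact, so that the denominator covers the same time as the counted events.
2. State that the per-subject count is an on-treatment measure. Step 1 repairs the rate but leaves this count unchanged.
3. Add a supplementary table of all AEs from first dose to Week 16+3 days regardless of IMP status, with time in trial over that window as denominator.

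The cost is some wording and one extra table from data already collected. If observation time would otherwise have included off-treatment weeks, the main rates will come out slightly higher. Off-treatment AEs in the new table may reflect rescue or other therapy, so it should be read beside the on-treatment table and not in place of it.
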